8.3.3.3 EXPECTEDNESS

Expectedness of each event will also be assessed to determine whether it is unexpected (e.g., nature not consistent with the intervention in the protocol, consent form, or other related materials) or expected (event is known to be associated with the provided intervention of this study).

8.3.4 TIME PERIOD AND FREQUENCY FOR EVENT ASSESSMENT AND FOLLOW-UP Any findings which consist of Adverse Events (AE), Serious Adverse Events (SAE) or Unexpected Problems (UP) will be documented on the appropriate Case Report Forms. All AEs, SAEs, UPs, regardless of severity, will be recorded. Potential untoward or unfavorable medical/dental occurrences that occur in a study participant, including any abnormal sign, symptom, or disease (including but not limited to dental pain, dental infection, trauma or other conditions that require immediate attention) that is temporally associated with the subject's participation in the research study (whether or not considered related to the subject's participation in the research) will be identified by all research team members at completion of each study visit and promptly reported to the PI. The PI will record the report on an adverse occurrence report sheet. The PI will also review all reports to determine whether the event is:

- 1) unexpected;
- 2) related or potentially related to research study participation; and/or
- 3) suggests that the research places subjects or others at a greater risk of harm related to the research than was previously known or recognized.

If these three conditions exist, the occurrence will be considered an UP and will be reported to the IRB on the appropriate form and to the NIDCR per their required timeframes. Unanticipated problems will be reported to the DSMB as part of the DSMB reports.

Through these reviews of AEs and occurrences, the DSMB will consider whether cumulative data indicates the need to change the research design, to modify information presented to participants, or to terminate the project. It is anticipated that the committee may decide that due to minimal risk in this behavioral study, there is not a risk for severe AEs that would require a-priori stopping rules (this decision will be reviewed at least annually by the DSMB). Any action taken to suspend or terminate the project will be reported to the UI IRB, the NIH Office of Sponsored Projects, and the program directors at NIDCR. New, scientific developments outside the study that may impact participant safety or the ethics of the study are considered in making these determinations. In addition, in following up AEs, SAEs, UPs, attempts will be made to obtain as much information as possible about event evolution and outcome. Every effort will be made to follow the subject until resolution of the event.

8.3.5 ADVERSE EVENT REPORTING

For all AEs that are deemed expected and/or unrelated to the study, a summary will be submitted to the NIDCR Program Officer with the annual progress report, as well as to the UI IRB at the annual continuing review. Adverse events will also be reported to the DSMB as part of DSMB reports.8.3.6 Serious Adverse Event Reporting

Any AE meeting the specified SAE criteria will be submitted on an SAE form to NIDCR's centralized safety system via Rho Product Safety. This report will be sent by fax or email. Once submitted, Rho Product Safety will send a confirmation email to the investigator within 1 business day. The investigator should contact Rho Product Safety if this confirmation is not received. This process applies to both initial and follow-up SAE reports. SAE Reporting Contact Information:

- Product Safety Fax Line (US): [name]
- Product Safety Fax Line (International): [contact]
- Product Safety Email: rho [contact]

General questions about SAE reporting can be directed to the Rho Product Safety Help Line (available 8:00AM – 5:00PM Eastern Time):

- US: [name]
- International: [contact]

The study's clinically responsible individual (the PI) will complete a SAE Form and submit via fax or email within the following timelines:

• All deaths and immediately life-threatening events, whether related or unrelated, will be recorded on the SAE Form and submitted to Product Safety within 24 hours of site awareness.

• SAEs other than death and immediately life-threatening events, regardless of relationship, will be reported within 10 days of site awareness.

All SAEs will be followed until resolution or stabilization.

In addition to being reported to NIDCR, all SAEe will be reported to the UI IRB within 10 business day of the investigator becoming aware of the event. The investigator will submit a Reportable Event form in the electronic IRB submission system at the UI.

8.3.7 REPORTING EVENTS TO PARTICIPANTS

If the study is prematurely terminated or suspended, study participants will receive written notification documenting the reason for the study changes.

8.3.8 EVENTS OF SPECIAL INTEREST NA

8.3.9 REPORTING OF PREGNANCY

NA

8.4 UNANTICIPATED PROBLEMS

8.4.1 DEFINITION OF UNANTICIPATED PROBLEMS

The Office for Human Research Protections (OHRP) considers UPs involving risks to study participants or others to include, in general, any incident, experience, or outcome that meets **all** of the following criteria:

- unexpected in terms of nature, severity, or frequency given (a) the research procedures that are described in the protocol-related documents, such as the IRB-approved research protocol and informed consent document; and (b) the characteristics of the participant population being studied;
- related or possibly related to participation in the research ("possibly related" means there is a reasonable possibility that the incident, experience, or outcome may have been caused by the procedures involved in the research); and
- suggests that the research places participants or others at a greater risk of harm (including physical, psychological, economic, or social harm) than was previously known or recognized.

8.4.2 UNANTICIPATED PROBLEMS REPORTING

Incidents or events that meet the OHRP criteria for UPs require the creation and completion of an UP report form. We will include the following information when reporting an UP, or any other incident, experience, or outcome to the IRB:

- appropriate identifying information for the research protocol, such as the title, investigator's name, and the IRB project number;
- a detailed description of the AE, incident, experience, or outcome;
- an explanation of the basis for determining that the AE, incident, experience, or outcome represents an UP;

• a description of any changes to the protocol or other corrective actions that have been taken or are proposed in response to the UP.

To satisfy the requirement for prompt reporting, UPs will be reported using the following timeline:

- UPs will be reported to the IRB within 10 business days of the investigator becoming aware of the event. The investigator will submit a Reportable New Information form in the UI (HAWK-IRB) electronic IRB submission system.
- All UPs will be reported to appropriate institutional officials (as required by an institution's written reporting procedures), the supporting agency head (or designee), and OHRP within one month of the IRB's receipt of the report of the problem from the investigator.

All UPs will be reported to NIDCR concurrently with reporting to the IRB. These reports will be made to NIDCR's centralized reporting system via Rho Product Safety:

- Product Safety Fax Line (US): [name]
- Product Safety Fax Line (International): [contact]
- Product Safety Email: [contact]

General questions about UP reporting can be directed to the Rho Product Safety Help Line (available 8:00AM – 5:00PM Eastern Time):

- US: [name]
- International: [contact]

8.4.3 REPORTING UNANTICIPATED PROBLEMS TO PARTICIPANTS

If any unanticipated problems occur that may affect the participant's decision to continue participation in the study, study participants will be notified. Safety monitoring for this study will focus on parameters that capture risks related to study participation. The study will collect UPs, including UPs that are also AEs and SAEs (Title 45 of the Code of Federal Regulations [CFR] Part 46). If the study is prematurely terminated or suspended, study participants will receive written notification documenting the reason for the study changes.

Version 0.7 2 July 2024

9 STATISTICAL CONSIDERATIONS

9.1 STATISTICAL HYPOTHESES

- Primary Efficacy Endpoint(s):
 - Lower caries incidence
- Secondary Efficacy Endpoint(s):
 - Better knowledge, behavior towards the child's oral health, and levels of salivary MS and visible plaque scores

9.2 SAMPLE SIZE DETERMINATION

Based on a sample size of 317, we should be able to entertain up to 31 covariates in a multiple regression model without jeopardizing model validity through overfitting (we note that this far exceeds the number of covariates targeted in this application, even allowing for reasonable examination of first-order interactions); this number would be smaller for logistic modeling, depending upon the distribution of the outcome variable. Finally, we note that modeling of outcomes such as clinical status and behavioral change can include covariates such as knowledge, behavioral intent, autonomy, competence, and relatedness. Such models incorporate the key aspects of the SDT intervention, can assist in the evaluation of the impact of SDT, and can offer validation of its application. The rich data set will permit formal evaluation of the validity of the theoretical basis of the proposed intervention, e.g., by evaluation of timing of behavioral change and whether it persists as prescribed by SDT, by assessing the relationships between outcomes and ratings of autonomy, competence and relatedness, and more systematically by use of mediation models.⁵⁸⁻⁶² While every effort will be made to maximize retention as outlined below, missing data issues will be addressed via multiple imputation^{63,64} the importance and utility of this approach have been substantiated for intervention trials targeting early childhood caries.⁶⁵ We will follow the general recommendations of Rubin^{66,67} and emulate the more specific aspects of execution of the caries-oriented analysis applied to these reported caries intervention trial data.⁶⁵ The possibility of selective dropout between the two groups will be fully explored, as will characteristics associated with dropout; sensitivity analyses will be conducted to explore the potential impact on results.

Power and Sample Size Considerations: Estimation of Detectable Effect Sizes

For purposes of sample size calculation, the primary outcomes of interest are caries status as measured by the d_{1-2-3} mfs and d_{2-3} mfs indices at the third-year follow-up, i.e., at approximately three years of age; caries status at two-year follow-up represents a secondary outcome. Indices are derived from the modified d_1d_{2-3} mfs caries criteria. Required sample sizes are primarily based upon the experiences reported by Wagner et al,⁶⁸ which were felt to provide the most appropriate estimates of effect sizes and variability after translation from the WHO caries criteria. Therefore, assuming an effect size (treatment difference) of 1.1 (standard deviation 3.45) for the number of cavitated, missing or filled lesions, Type I error level of 0.05, and 80% power, required sample size is 156 children per group at the three-year follow-up. Given enrollment of 317 mother-child dyads for each group (experimental (SDT) video or neutral control), and a conservative annual attrition rate of 21%, 156 dyads per group (312 total) would be expected to

complete three-year follow-up. Based upon these sample sizes, we would have 93% power to detect a treatment difference of 1.7 (given s.d. of 4.35) if the caries index also included white spot lesions, based on the observations of Wagner et al.⁶⁸ As described in the previous section, somewhat more optimistic retention rates may be realistically anticipated: if we assume an attrition schedule of 21% the first year and 15% for each of the two subsequent years, we would anticipate that initial recruitment of 317 dyads per group would result in about 180 dyads per group completing 3-year follow-up, corresponding to 85% power to detect a 1.1 difference in d₂₋ 3mfs and 95% power to detect a 1.7% difference in d₁d₂₋₃mfs. Sensitivity analyses drew upon available data on children aged 26-30 months from our WIC-based studies in three Eastern Iowa Cities^{10,11,50-52,69} and the literature. Our studies^{10-13,49-54} suggest the standard deviation of both of these indices is slightly less than 3.0 surfaces, which would be expected to result in slightly higher power estimates that those given above; however, we will be drawing from a wider geographic area of the state, and somewhat greater variability has been reported for other WIC populations.^{70,71} We note that we have adequate power to detect smaller effect sizes than were noted at two years in the intervention trial of Harrison et al⁷² comparing the effect of motivational interviewing and control on ECC; moreover, they are similar to, or less than, the observed but non-significant differences for caries outcomes in a smaller study among First Nations children that also compared the effects of MI counseling vs. control.⁷³ They will also provide some protection against loss of power should response rates be less than projected or in the case of misspecification of the statistical assumptions.

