8 STUDY ASSESSMENTS AND PROCEDURES

8.1 ENDPOINT AND OTHER NON-SAFETY ASSESSMENTS

Endpoints

The primary outcome of interest is caries status, which will be measured by the d₁d₂₋₃mfscaries criteria for scoring dental caries for the children^{44,45-49} Both d₁mfs and d₂₋₃mfs scores derived from these criteria will be considered, reflecting numbers of affected (cavitated, missing due to caries or filled) surfaces with and without inclusion of non-cavitated (d₁ "white spot") lesions. These caries outcomes will be assessed by dental examinations at 12, 24 and 36 months of age. Secondary outcomes of interest will assess changes in maternal knowledge and oral health behaviors through questionnaires via REDCapTM, as well as children's plaque and microbial outcomes through dental exams and plaque collection done by dental providers who will be blinded to study allocation.

Screening and Enrollment

• The PI and CTRA are responsible for tracking the screening, enrollment, and the number approached, refusals and reasons for refusal. The UI Institute for Clinical and Translational Science IT specialist along with the Database Manager will provide combined enrollment reports of all the WIC sites to the study team and NIDCR.

Visit Procedure Completion

• The study CTRA and RAs are responsible for collecting the data at the WIC sites during visits 1, 2, 3 and 4. Participants will view videos and complete questionnaires on tablets/i-pads through REDCapTM. UI dental providers will conduct dental exams and collect plaque samples for all participating children. The REDCapTM system will ensure that once a study participant is randomly assigned to one of the two study groups, based on the participant language preference (English vs. Spanish), the participant will be linked to her assigned group and study activities in all time points throughout the duration of the study. In addition, the REDCapTM will also allow us to do complex and robust multivariate data checks, which will be critical for flagging the study team for potential issues within the data or potential process issues at the study sites. The Database Manager will provide reports of number of visits completed for each WIC sites.

Retention and Attrition

• The study PI and CTRA are responsible for tracking the recruitment, retention and attrition status throughout the study. Efforts will be made to assess reasons for dropouts.

Data Entry Errors

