9.4.2 ANALYSIS OF THE PRIMARY ENDPOINT(S)

Primary efficacy

The primary outcome is caries status, measured by the d_1d_{2-3} caries criteria for scoring dental caries in children developed by members of the Iowa Fluoride Study. Caries status as total counts of dmf surfaces will be calculated during yearly dental exams. These counts will be reported as means, medians, quartiles, standard deviations, and ranges for each intervention group. Data will be explored longitudinally using dmf surfaces at each age and dmf increments between ages. Analysis of caries outcomes will focus on Poisson and/or negative binomial modeling, possibly with variance inflation and zero inflation accommodation, as appropriate. To account for repeated longitudinal measurements, generalized estimating equations (GEEs) will be used to model these counts. A first-order autoregressive or AR(1) working correlation structure will be

assumed. The quasi-likelihood information criteria (QIC) will be used to compare models to select the best fit. The model will include age, gender, location (urban/rural), race, intervention, and mothers' knowledge and behavior. These are all clinically important known covariates that are associated with caries status, and mothers' intervention and behavior/knowledge are covariates of interest. These are planned covariates to include; however, if the number of covariates is limited by the sample size or infrequent observations of caries, we will use bivariate analyses to inform a more parsimonious final model. Results for the model will be presented as incidence rate ratios with 95% confidence intervals. Data will be analyzed on an intention-to-treat basis with sensitivity analyses considering the per-protocol dataset. Missing data will be addressed via multiple imputation and sensitivity analyses will be conducted to explore potential impacts on results.

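### Section 9.2 names two primary caries indices, each powered at the full two-sided 0.05, and nothing in the protocol says which one decides the trial

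*Protocol*

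**What the plan says.** **Protocol 9.2 (Sample Size Determination)** uses the plural: "the primary outcomes of interest are caries status as measured by the d_{1-2-3} mfs and d_{2-3} mfs indices at the third-year follow-up". The same sentence makes the two-year result secondary, so the authors ranked the exam ages but not the indices. The sample size is then set on cavitated, missing or filled lesions (difference 1.1, SD 3.45): "Type I error level of 0.05, and 80% power, required sample size is 156 children per group at the three-year follow-up". For the wider index, "we would have 93% power to detect a treatment difference of 1.7 (given s.d. of 4.35) if the caries index also included white spot lesions". With about 180 completers per group, the section gives 85% and 95% power for the two indices.

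**Protocol 8.1** (and the synopsis, 1.1, in similar terms) derives two scores, "reflecting numbers of affected (cavitated, missing due to caries or filled) surfaces with and without inclusion of non-cavitated" lesions, and says only that the "scores derived from these criteria will be considered".

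**Protocol 9.4.2** returns to the singular: "The primary outcome is caries status, measured by the" d1d2-3 criteria. It continues: "Caries status as total counts of dmf surfaces will be calculated during yearly dental exams". That could be either score.

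No section gives a testing order, an alpha split, a requirement that both succeed, or a statement that one is enough. The Section 3 objectives table is broken in the available text, so nothing is drawn from it.

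**The concern.** The two indices measure different things and can disagree. On the protocol's planning values, 1.7 - 1.1 = 0.6 surfaces of the expected difference on the wider index, about 35%, comes from white spots. The intervention could shift early lesions and leave cavitation unchanged, or the reverse could appear by chance. The protocol does not say whether a significant result on only one index is a positive trial.

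Two things are at stake. First, the stated 0.05 describes each test, and whether it also describes the primary claim depends on an unstated decision rule. Second, a result on white spots alone could be reported as the primary finding of caries prevention, although the sample size was justified on the cavitated index. Sections 7.1 and 10.1.2 also list attainment of the primary endpoint, in the singular, among the grounds for stopping. That presupposes one endpoint with one criterion.

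**Working it through.** **Inputs from Section 9.2.** d2-3mfs: difference 1.1, SD 3.45. Index with white spots: difference 1.7, SD 4.35. Alpha is 0.05, with sidedness not stated. Enrolment is 317 per group. Attrition is 21% a year, or 21% then 15% and 15%. Allocation is 1:1 (9.4.1). The protocol gives no correlation between the indices.

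**Step 1: reproduce the plan's figures** (comparison of two means, normal approximation).

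- n per group = 2 × [(1.960 + 0.842) × 3.45/1.1]² = 154.4, so 155 (stated 156). One-sided alpha would give 122, so the plan is two-sided.
- Retention: 317 × 0.79³ = 156.3; 317 × 0.79 × 0.85² = 180.9.
- Standardized difference at n = 156: 1.1/(3.45 × √(2/156)) = 2.816 and 1.7/(4.35 × √(2/156)) = 3.451.

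| Completers per group | Index | Stated power | At 0.05 | At 0.025 |
|---|---|---|---|---|
| 156 | d2-3mfs | 80% | 80.4% | 71.7% |
| 156 | with white spots | 93% | 93.2% | 88.7% |
| 180 | d2-3mfs | 85% | 85.7% | 78.3% |
| 180 | with white spots | 95% | 96.0% | 92.9% |

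The stated figures match the full two-sided 0.05 on each index (to within about one point at 180) and do not match an even split. They contain no allowance for two primary tests.

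**Step 2: error if either index could carry the claim.** Under no effect on either index, treat the two test statistics as bivariate normal with correlation ρ. Then the error is 1 - P(|Z1| < 1.96 and |Z2| < 1.96).

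| ρ | 0 | 0.5 | 0.7 | 0.8 | 0.9 | 0.95 |
|---|---|---|---|---|---|---|
| Error | 9.75% | 9.1% | 8.35% | 7.8% | 7.0% | 6.5% |

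One value of ρ can be tied to the planning figures. The wider index W is the cavitated index C plus the white-spot count D. If C and D are uncorrelated, corr(C, W) = SD(C)/SD(W) = 3.45/4.35 = 0.793, and the error is 7.85%. If corr(C, D) runs from -0.3 to +0.5 with the same two SDs, ρ runs from 0.53 to 0.96 and the error from 9.0% to 6.3%.

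Counting only false claims of benefit (2.5% per test), the either-index risk at ρ = 0.793 is about 3.9%.

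**Step 3: error and power if both had to succeed.** The error cannot exceed that of one test, so there is no inflation. Under the planned effects at 156 per group and ρ = 0.793, the chance that both tests are significant is 79.3%, and that at least one is, 80.4% + 93.2% - 79.3% = 94.3%.

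**Step 4: cost of an even split.** For 80% power on d2-3mfs at 0.025, n = 2 × [(2.241 + 0.842) × 3.45/1.1]² = 187.0 completers per group. Dividing by 0.79³ = 0.493 gives about 380 enrolled per group, against 317.

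**The case against.** A reader might infer that a significant result on either index is, as written, a positive trial with an error of about 8%. The documents do not support that. No section says that one index is enough. Section 9.4.2 speaks of a single outcome, and a rule requiring both indices fits the text equally well with no inflation. The statistical analysis plan is not shown, and testing order or alpha allocation may be set there.

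Nor is 8% a protocol figure. It depends on an assumed correlation, and 3.45 and 4.35 derive from an outside study. Section 9.2 also reports that in the team's own data both indices have SDs slightly below 3.0. On the same ratio argument, nearly equal SDs put the correlation near 1 and the error near 5%. The calculation compares means at one exam, whereas 9.4.2 plans count models over repeated exams, for which the correlation of the test statistics is unknown. Counted as false claims of benefit only, the risk is 3.9% against 2.5%.

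It can also be said that the sample size rests on d2-3mfs alone, and that the white-spot power is only what that sample happens to provide.

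All of this limits the size of the problem and rules out a single unconditional error rate. It does not remove the inconsistency. The protocol itself names two primary outcomes in 9.2 and one unspecified outcome in 9.4.2, and a later analysis plan that chose one index would depart from 9.2. That the sample size rests on d2-3mfs is a good reason to make it the deciding index, but the protocol does not do so.

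**Conclusion.** The point holds as an unclear primary designation, and it should be fixed. Two indices are primary in Section 9.2, each powered at the full two-sided 0.05, and no section says which decides success or how error is controlled across them. The stated 5% is therefore not assured for the primary claim.

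The size depends on a rule the protocol does not state. Under an either-index rule, the two-sided familywise error is roughly 6% to 10% over the correlations examined. The 7.85% figure requires uncorrelated white-spot and cavitated counts and the planning SDs. Under a both-indices rule, error is controlled and the cost is joint power of about 79%. These figures assume approximately normal tests at the three-year exam. That the protocol leaves the rule open does not depend on any of them.

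**What to change.** In Sections 1.1, 3, 8.1, 9.2 and 9.4.2, name the d2-3mfs count at the 36-month exam as the single primary endpoint, since the 156 per group is computed for it. Make the index including white spots the first secondary endpoint, tested at two-sided 0.05 only if d2-3mfs is significant. State in 9.2 that the 93% and 95% power figures belong to that secondary test.

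This keeps the 5% error level, the 80% power and the enrolment of 317 per group. It needs a protocol amendment, because one declared primary outcome becomes secondary, but no new data or procedures. The price is that an effect on white spots alone could no longer be called a primary success. If the sponsor wants both indices to remain primary, the alternatives are to require both (about 79% joint power at 156 per group under the 0.79 assumption) or to split alpha evenly (about 72% and 89% power at 156, or about 380 enrolled per group to keep 80% on d2-3mfs). Whichever rule is chosen should be stated in the protocol.
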